## Hold Parameters for Study Arm subjects on ARB:

- Hold dose for SBP <100, re-check SBP in 10 min. If SBP remains <100, hold dose and call MD.
- 2. Hold dose and call MD, if potassium level increases >5.0.
- 3. Hold dose and call MD, if creatinine clearance drops below 30ml/min during treatment.

## Parameters to meet to discontinue ARB study treatment for subjects on ARB:

- 1. Progression to mechanical ventilation.
- 2. Occurrence of acute renal impairment any time during treatment. This is defined as a 50% reduction in GFR from baseline.

**Procedure Classification:** Aside from a pregnancy test for subjects of childbearing potential, there are no other extra tests, imaging scans or procedures that will be performed as part of the study.

Potential Hazards and Precautions: There are no perceivable potential hazards to the subject.

**Study Timeframe:** The study time frame would be from IRB approval date to the end of the pandemic or until our sites reach 200 subjects, whatever comes first.

The end of study for each individual subject will be the date of discharge from the Sharp Healthcare hospital. The subject will not be followed if there is a transfer to a non-Sharp hospital or any sub-acute care setting (i.e. SNF, LTAC, rehabilitation center). If the subject is discharged prior to the 10th day of treatment of the ARB, the ARB is not to be continued after the subject is discharged from the Sharp Healthcare hospital.

**Method of Subject Identification and Recruitment:** The PI or Sub-I will be notified of a COVID-19 confirmed positive patient via hospital generated alert as part of the Infectious Disease Team at each hospital.

**Subject Capacity:** Subjects who do not have the capacity or an appropriate LAR to provide written informed consent will not be enrolled in the study.

**Subject/Representative Comprehension:** Subjects/LARs must have the ability to understand the requirements of the study, provide informed consent, and provide authorization of use and disclosure of personal health information. Subjects with impaired cognitive or decision-making capacity (based on the clinical judgment of the PI or designee) must have an appropriate LAR to provide consent on their behalf.

**Documentation of Consent/Assent:** Consenting will be conducted as described above in the Procedures and Study Visits section. Consents will be printed and stored in the subject's research binder in a secure location.

Reimbursements or Payments: None

Costs to the Subject: None

**Data Sources:** Sharp HealthCare electronic medical records (EMR) for hospital inpatients who meet inclusion criteria at acute care facilities.

**Data Collection/ Assessment Instruments:** The Case Report Form will include the following data elements: Demographics (age, gender, race/ethnicity, insurance), medical status (pre-existing comorbid conditions (based on the Charlson Comorbidity Index). The tool used to calculate the Charlson Comorbidity Index can be found here

https://www.mdcalc.com/charlson-comorbidity-index-cci#next-steps). Other data to be collected includes vital signs, serum creatinine, calculated creatinine clearance (Cockroft and Gault equation), white blood cell count, platelet count, maximum body temperature in the past 24 hours, serum potassium level, serum sodium level, oxygen demand rate, and BSA. Receipt of interventions will include use of mechanical ventilation and duration, oxygen requirements, whether or not there is an admission to the ICU, any concomitant antimicrobials including azithromycin, doxycycline, hydroxychloroquine, chloroquine, and remdesivir. Measures of

COVID-ARB PROTOCOL VERSION 3.0, DATED 20APR2020

healthcare service utilization will include length of stay, number of days in ICU, number of days requiring oxygenation, discharge disposition and mortality.

**Data Collection Resources:** The Study Coordinator will complete the Case Report Forms, with assistance from Sharp's Clinical Analytics team to extract information from the EMR.

**Data Analysis:** Descriptive statistics will be conducted to describe frequencies of demographics and clinical characteristics including the following: age at discharge, gender, race/ethnicity, payer, comorbid conditions based on the Charlson Comorbidity Index, receipt of medical interventions (mechanical ventilation, medications) and healthcare service utilization (ICU admission and Length of Stay in the hospital). Frequencies and descriptive statistics will be conducted using chi-square or 2-tailed Fisher exact statistics depending on the final sample size for categorical data and t-tests for continuous data.

**Privacy of Subjects:** There will be limited access to the subject due to standard of care isolation protocols. The Informed Consent process will emphasize the personal nature and privacy concerns related to communications regarding the subject's condition and infectious disease test results.

**Confidentiality of Data and Storage:** All binders will be stored and secured at Sharp's Center for Research office in accordance with all regulatory and organizational requirements, and will be accessed only by authorized personnel. No subject-specific data will be reported. Sharp medical record number will be used to link subject records across data systems and hospital visits. Protected Health Information (PHI) will be safeguarded as specified by Sharp HealthCare policy. There is a risk of disclosure of PHI from inappropriate access to the study database. All efforts will be made to protect PHI, including password protecting the database with access only allowed to study members who are Sharp HealthCare employees. All datasets will be de-identified prior to any statistical analyses conducted by the Statistician. Identifiers will be destroyed two years after study end date, once data has been aggregated for reporting.

**Data Monitoring:** Study data will be monitored by the PI and physicians on the study team for frequency of hypotension, hyperkalemia, acute renal impairment, liver dysfunction, rates of ICU transfer, rates of respiratory failure requiring mechanical ventilation. The following team will review the data at intervals of 25%, 50%, and 75% target enrollment:

- [name], MPH (Biostatistics/Epidemiology)
- [name] (Critical care)
- [name] [name] (hospitalist)
- [name] (hospitalist)

If disproportionate higher rate of complications is observed in one arm of the study over the other at any interval based on the clinical review, a biostatistician will be consulted for confirmation. If such disproportionality is considered biostatistically significant, study enrollment will cease.

**Benefits to Individual Subjects:** Potential reduction in ICU hospitalization, potential avoidance of mechanical ventilation and potential decrease in length of stay in the hospital.

**Potential Benefits (Value) to Society:** Any data collected will be a benefit to society whether we prove or disprove the hypothesis. However, if it is determined that the studied intervention indeed does reduce demand for mechanical ventilation and ICU care, it may provide significant relief to a medical care system that is anticipated to be overwhelmed at pandemic peak. The benefits will most likely be realized in the next SARS-CoV-2 epidemic. There are potential benefits to each institution that participates in this study to reduce the demand of mechanical ventilation and reduce the demand for isolated negative pressure ICU rooms.

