To date (17MAR2020), there have been very few human studies analyzing the effects of utilizing ARBs in the critical care setting where subjects have confirmed COVID-19 infection. The COVID-19 epidemic has already claimed more human lives than SARS and MERS combined (WHO website MAR-2020). The majority of fatalities from COVID-19 have resulted from respiratory failure.

Data has accumulated since the 2002 SARS epidemic that use of angiotensin receptor blockers may be beneficial in reducing SARS-induced respiratory failure, as summarized recently (Gurwitz, *Drug Dev Res* 04MAR2020).

It is currently believed that 80% of COVID-19 subjects will require no medical treatment, 15% will require non-ICU medical care, and 5% may require ICU admission. The goal of this study is to decrease the rate of subjects requiring ICU hospitalization and decrease the demand for mechanical ventilation.

ARBs may prevent respiratory complications for two reasons. First, ARBs compete with the coronavirus's binding site in the lung. That, in turn, has been shown to decrease the damage to the lung. Second, the ARBs decrease the inflammatory response in the lung that the coronavirus causes. By these two mechanisms, the ARBs decrease the lung damage and allows the body (host) to effectively and naturally fight against the virus.

## Number of Subjects: 200

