## **Exclusion Criteria:**

- 1. Severe allergy to any ARB, including angioedema and ACE inhibitor-induced angioedema
- 2. In the intensive care unit at screening.
- 3. Home meds include any kind of ACE inhibitor or ARB
- 4. Acute Kidney Injury (50% reduction in GFR from baseline at admission to any time during treatment in the study treatment arm)
- 5. Hyperkalemia >5.0 mmol/L at baseline or any time during treatment in the study treatment arm
- 6. Creatinine Clearance < 30 ml/min at baseline or any time during treatment in the study treatment arm

Age of Subjects: >18 yrs of age

Gender of Subjects: Either male or female

Racial and Ethnic Origin: Non-specific

Vulnerable Subjects: Hospitalized subjects

**Study Design:** Investigator initiated, open label, multicenter, two arm, randomized study to compare the impact of adding an ARB to the Standard of Care (SOC) to the SOC without an ARB. Randomization ratio will be 1:1.

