- ii. If feasible, the subject/LAR or hospital staff or CRC (if on a video call) will take a picture of the informed consent document signature pages to be saved with the copy of the consent signed by the CRC in the study records. If this is not feasible, the CRC will sign the consent and the witness and CRC will provide a dated attestation to be saved in the study records confirming that the subject/LAR agreed to participate in the study and signed the informed consent. The CRC will email the participant a copy of the consent that the CRC signed, including the witness and CRC attestation (if applicable). The CRC will also email the participant the photograph of the signature pages that the participant signed, if pictures were taken.
- c. If feasible, the LAR may be consented in person in a private setting by the CRC.
- The designated research team member will randomize the subject. The randomization will be computer generated using this website in blocks of 4 (https://www.sealedenvelope.com/simple-randomiser/v1/lists).
- 6. If the subject is randomized to the "study arm", then the Research Pharmacy will enter in the order for the chosen ARB starting dose and will not charge the subject. If the subject is randomized to the SOC arm, there is no additional work to be completed by the Research Pharmacy.
- 7. If the subject is randomized to the "study arm" and already on established antihypertensive therapy other than ACE inhibitors or ARB (which would be exclusionary), it will be up to the treating physician's discretion to hold or reduce the dose of this treatment(s) in order to allow tolerability of ARB intervention depending on the blood pressure.
- If the subject is randomized to the "study arm" a pregnancy test will be ordered as necessary for subjects of childbearing potential who have passed all the other screening criteria.
  - a. Dosing Schemata LOSARTAN is the first choice of ARB in this study and will continue based on availability. ARB alternatives are listed below: 10 days of treatment with losartan
    - i. Dose 1 and 2\*: Losartan 12.5mg PO BID for all subjects. The first AM dose can be given up to 1:00pm on Day 1.
    - ii. Dose 3 and 4 :
      - PI or delegee has the option to increase losartan dose to 25mg PO BID for subjects with a calculated creatinine clearance of >40ml/min provided the clinician is confident that the subject will

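### No covariate-adjusted between-arm analysis is prespecified, although age, comorbidity and oxygen demand are on the case report form; the cost is precision, not validity, and its size depends on how prognostic those variables are.

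*Combined protocol and SAP*

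**What the plan says.** All references are to the combined protocol and SAP.

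- **Data Analysis** names the only tests in the plan: "Frequencies and descriptive statistics will be conducted using chi-square or 2-tailed Fisher exact statistics" for categorical data and "t-tests for continuous data". The variables listed in that paragraph include mechanical ventilation and ICU admission. No regression, stratified test or other adjusted analysis appears there or elsewhere.
- **Data Collection/ Assessment Instruments** lists "Demographics (age, gender, race/ethnicity, insurance" and so on, comorbidity by the Charlson index, and "serum potassium level, serum sodium level, oxygen demand rate, and BSA". No time point is given for the oxygen value. Data Analysis describes age at discharge, includes Charlson comorbidity, and does not mention oxygen demand rate.
- **Study Design** describes an "Investigator initiated, open label, multicenter, two arm, randomized study" and adds "Randomization ratio will be 1:1".
- **Procedures and Study Visits**: "The randomization will be computer generated using this website in blocks of 4". No stratification by hospital, age or severity is stated.
- The sample size is given as "Number of Subjects: 200", with no alpha, power, event rate or effect size.

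**The concern.** The paragraph is headed and worded as description, but ventilation and ICU admission are among its variables and they carry the primary and secondary objectives. No other between-arm test exists, so these unadjusted tests are in effect the efficacy analysis.

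Age and oxygen demand are plausible predictors of ICU transfer and ventilation. If they do predict outcome, leaving them out makes the interval for the treatment effect wider than it need be. It also leaves the observed difference uncorrected for whatever imbalance chance has produced.

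Timing matters too. The trial is open label, and Data Monitoring has the study team review ICU transfer and ventilation rates at 25%, 50% and 75% of enrolment. A covariate model chosen after those reviews would be open to the charge of having been picked from the data; one fixed now would not.

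**Working it through.** **The plan's own figure.** The 200 cannot be reproduced, because no design inputs are given. For orientation, 100 per arm at two-sided alpha 0.05 has 80% power for 25% vs about 10%, or 20% vs about 6.6%.

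**Inputs**
- From the documents: 200 subjects at 1:1, so n = 100 per arm.
- Assumed: two-sided alpha 0.05, no dropout.
- Assumed control rate 25%. The background section expects 15% of cases to need ordinary hospital care and 5% to need ICU care; 5/(15+5) = 25%. Halving it to 12.5% is an assumption.
- Assumed rarer endpoint, nearer to ventilation: 10% vs 5%.
- Assumed covariate strength: R-squared 0 to 0.25.

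**Formula.** Power = Φ[(d − 1.96·SE0)/SE1], where d = p1 − p2, SE0 = √(p̄(1−p̄)·2/n) and SE1 = √((p1(1−p1) + p2(1−p2))/n). Adjustment is approximated by replacing n with n/(1−R²).

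*25% vs 12.5%, unadjusted:* p̄ = 0.1875, SE0 = 0.0552, SE1 = 0.0545. (0.125 − 1.96×0.0552)/0.0545 = 0.31, so power is 62.1%.

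*The same with R² = 0.25:* n becomes 100/0.75 = 133.3, SE0 = 0.0478, SE1 = 0.0472. (0.125 − 1.96×0.0478)/0.0472 = 0.66, so power is 74.7%, or 12.5 points more before rounding.

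*10% vs 5%, unadjusted:* p̄ = 0.075, SE0 = 0.03725, SE1 = 0.03708. (0.05 − 1.96×0.03725)/0.03708 = −0.62, so power is 26.7%.

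| R² | Effective n per arm | Gain, 25% vs 12.5% | Gain, 10% vs 5% |
|---|---|---|---|
| 0 | 100 | 0 | 0 |
| 0.05 | 105.3 | +2.2 | +1.2 |
| 0.10 | 111.1 | +4.6 | +2.5 |
| 0.15 | 117.6 | +7.1 | +3.9 |
| 0.20 | 125.0 | +9.8 | +5.5 |
| 0.25 | 133.3 | +12.5 | +7.3 |

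(Gains in percentage points of power.)

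**Simulation check** (3000 runs per scenario, uncorrected chi-square against the adjusted logistic likelihood-ratio test, 25% vs 12.5%):

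| AUC | R² | Chi-square | Adjusted | Gain |
|---|---|---|---|---|
| 0.50 | 0.00 | 63.9% | 64.3% | +0.4 |
| 0.63 | 0.04 | 63.3% | 65.4% | +2.1 |
| 0.74 | 0.15 | 63.4% | 69.0% | +5.6 |
| 0.82 | 0.26 | 63.6% | 74.6% | +11.0 |

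The simulated gains are a little below the approximation at the stronger end. At 10% vs 5%, a two-covariate simulation with AUC 0.71 to 0.84 moved power from about 26–28% to 29–34%, a gain of 3 to 7 points.

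**Validity.** With 25% in both arms, rejection was 4.9–5.0% for chi-square, 3.3–3.4% for Fisher and 4.8–5.2% for the adjusted test. With about 10% events the adjusted test rejected about 6% of the time, against 5.4–5.9% for the unadjusted test.

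**Chance imbalance.** In SD units the difference in a covariate mean has standard error √(2/100) = 0.141. P(|difference| > 0.2 SD) = 2(1 − Φ(0.2/0.141)) = 15.7% for any one variable.

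**The case against.** The strongest reply is that nothing is wrong with the tests. Under randomisation they are valid and the null simulation bears this out. The 16% chance of a 0.2 SD imbalance is ordinary sampling variation that the unadjusted interval and p-value already allow for. This stands in full. A reader might infer bias or an inflated false-positive rate; the documents support neither.

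A reader might also take a fixed loss, such as 3 to 12 points, as a property of this plan. It is not. Every input except the sample size and allocation ratio is assumed. The top of the range needs two covariates with a joint AUC above 0.8, while eligibility is limited to mild to moderate symptoms outside the ICU, which may narrow the spread of severity. The larger gains also belong to the commoner, ICU-type event. At the rarer rates power stays low with or without adjustment.

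Third, the data may not be ready to use as listed. Oxygen demand has no stated time point, and age is described at discharge. A pre-randomisation oxygen value can probably be taken from the electronic record, but the plan does not say so. Nor is it right to say that all three variables serve only as descriptive tables, since oxygen demand is absent from the analysis list.

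Finally, it can be said that the plan designates no primary-endpoint test or alpha at all, and that this is the larger gap. That is fair. It does not remove this point, because adjustment should be settled when that test is written.

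**Conclusion.** The point holds as a matter of efficiency. Adjustment is a worthwhile and inexpensive improvement, not the correction of an error. On two-sided alpha 0.05 and 100 per arm, the gain is about 2 to 12 points of power at an assumed 25% vs 12.5% with R-squared of about 0.05 to 0.25. At an assumed 10% vs 5% it is about 2 to 7 points for R-squared of about 0.10 to 0.25, and nearer 1 point at 0.05. If the covariates do not predict outcome, the gain is about 0 and essentially nothing is lost.

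**What to change.** In Data Analysis:

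1. Make the main between-arm analysis of ventilation, and of ICU transfer, a logistic regression on arm plus one fixed covariate set: age at randomisation and the last oxygen demand rate recorded before randomisation, taken from the electronic medical record.
2. Report a standardised risk difference with 95% CI.
3. Analyse continuous outcomes by linear regression with the same covariates.
4. Keep the chi-square, Fisher and t-tests as supportive.
5. Do not let the observed event count choose the covariates. At 10% vs 5% the expected total is 10 + 5 = 15 events, and a rule that dropped a covariate below 15 would trigger in about 46% of trials (exact binomial). If sparse events are a concern, keep the same covariates and prespecify a penalised (Firth) likelihood.

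Two covariates keep the model small for the number of events that may occur.

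The cost is a few lines of analysis text and a case report form instruction tying the oxygen value to a time before randomisation. The small downside is that the adjusted likelihood-ratio test may be slightly liberal when events are few (about 6% in simulation at a 10% event rate).

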## **Risk Category:** Greater than minimal risk

**Potential Risks:** Hypotension and hyperkalemia would be the main risks of adding an ARB to the SOC.

## **Protection Against Risks:**

## Hold Parameters for Study Arm subjects on ARB:

- 1. Hold dose for SBP <100, re-check SBP in 10 min. If SBP remains <100, hold dose and call MD.
- 2. Hold dose and call MD, if potassium level increases >5.0.
- 3. Hold dose and call MD, if creatinine clearance drops below 30ml/min during treatment.

## Parameters to meet to discontinue ARB study treatment for subjects on ARB:

- 1. Progression to mechanical ventilation.
- 2. Occurrence of acute renal impairment any time during treatment. This is defined as a 50% reduction in GFR from baseline.

## Other protections against risks:

Monitoring of hypotension and hyperkalemia will be conducted by the patient care team in accordance with routine standard of care processes.

If the subject experiences side effects that are suspected to be due to the ARB for subjects in the study group, it will be up to the discretion of the treating clinician/critical care team/PI whether to continue the ARB or not. If the subject prematurely stops study treatment, the study team will continue to collect data until discharge.

Subjects who develop acute renal impairment whether or not the ARB is the causative agent during study treatment will be withdrawn from the study. Subjects may also be withdrawn if they develop liver dysfunction, based on physician's discretion.

For subjects who experience disease progression due to the coronavirus and are transferred into the critical care setting, it is up to the discretion of the critical care team and the PI whether or not to continue the ARB.
